- 4. Fundus Photography: In this study, no invasive procedure will be applied to the patient, and the retinal photography will be taken by the camera operator with a special non-mydriatic digital camera called a fundus camera. In some patients diagnosed with Retinow AI, pharmacological dilatation (mydriasis) using a dilatation solution may be required to obtain a fundus image of sufficient quality. The dilatation procedure will be performed only by healthcare personnel (general practitioners, nurses, etc.) who are competent and trained in this regard.
- 5. Recording of Images: Right and left fundus images of each participant will be taken and these images will be recorded by the responsible researcher. The principal investigator will download the images via the hospital's PACS system.
- 6. Analysis of Images: Fundus photographs will be analyzed by the Retinow AI device. Then, they will be analyzed by expert ophthalmologists for gold standard evaluation.

Revision Date	920	
Revision No	01.05.2023 V.00	
Issue Date		
Document No	TF.01.CIP.01	

8. Gold Standard Assessment: The gold standard assessment results performed by specialist doctors will be used to determine the sensitivity and specificity of the Retinow Al device.

Al Analysis: Retinow Al software will analyze the collected images within 24 hours of image acquisition. This rapid analysis will allow for a near real-time comparison with expert diagnoses.

Clinical data will be fed into Retinow Al software and the success metrics (Accuracy, Sensitivity, Specifity) will be evaluated. Diagnostic labels provided by Retinow Al software will be compared with labels provided by expert ophthalmologists. Performance metrics of accuracy, sensitivity and specificity will be calculated.

The clinical study will be completed when the predicted number of data is reached

9. Subjects

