P: It is used in statistical tests to determine whether the results are significant. In a hypothesis test, it shows how much the data deviates from the expected distribution and expresses the probability that the results occurred randomly.

True Positive (TP): This refers to the situation where the software correctly diagnoses the disease. That is, it occurs when the software classifies an actual disease as a patient.

True Negative (TN): This refers to the situation where the software does not correctly diagnose the disease. That is, it occurs when the software classifies an actual healthy state as healthy.

False Positive (FP): This refers to the situation where the software incorrectly diagnoses the disease. That is, it occurs when the software classifies an actually healthy condition as sick.

False Negative (FN): This refers to the situation where the software does not incorrectly diagnose the disease. So it happens when the software classifies a real disease as healthy.

These terms are used to evaluate the accuracy and precision of software in classifying a disease or condition. True Positive and True Negative results represent conditions that were correctly diagnosed, while False Positive and False Negative results represent conditions that were misdiagnosed. Below is the calculation of sensitivity, specificity and accuracy values in our clinical study.

```
Sensitivity = TP/(TP + FN)
Specificity = TN/(TN + FP)
Accuracy = (TN + TP)/(TN + TP + FN + FP)
```

The passing criteria for the Retinow AI software in the clinical study will be based on its accuracy, sensitivity and specificity in diagnosing diabetic retinopathy, glaucoma and macular degeneration. The passing criteria were determined as 90% accuracy, 90% sensitivity and 90% specificity for all diseases. These threshold values are necessary for the software to be used as a reliable diagnostic tool in the clinical setting. In addition, it will be mandatory for the reliability of the study and the validity of the results to be kept below 10% of the possible technical errors and data loss rates. When these criteria are met, Retinow AI will be considered successful; otherwise, the software will not pass the study.

Sample Size

The required sample size for each study whose results will be analyzed with Cohen's Kappa analysis was calculated using Arifin's [82] calculation tool, which was developed based on the formula presented by Donner and Eliasziw [81].

Document No	TF.01.CIP.01

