Issue Date	01.05.2023
Revision No	V.00
Revision Date	3 — 8

However, in order to provide additional safety margin against possible data loss and participant losses at each stage of the study, it was planned to conduct the study with 305 people for each disease (diabetic retinopathy, glaucoma and macular degeneration). In this way, the reliability of the data and the statistical validity of the results will be preserved. The sample size calculations made in the calculation tool are given below.

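### The below-10% ceiling pools technical errors with data loss and, on its most natural reading, fails the software for losses it did not cause

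*Combined protocol and SAP*

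**What the plan says.** The passing criteria are in Annex 1 (Statistical Analysis Plan), under Analytical Procedures, just before Sample Size. Three statements follow one another:

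- The performance thresholds: "The passing criteria were determined as 90% accuracy, 90% sensitivity and 90% specificity for all diseases".
- A further condition, introduced with "In addition, it will be mandatory for the reliability of the study and the validity of the results", which requires the study to be "kept below 10% of the possible technical errors and data loss rates".
- The consequence: "When these criteria are met, Retinow AI will be considered successful; otherwise, the software will not pass the study".

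Two other places bear on it. Section 8, step 5 (Recording of Images) has the images recorded by a researcher and then fetched from the hospital's image archive: "The principal investigator will download the images via the hospital". The Sample Size text in Annex 1 sets 305 people per disease as an "additional safety margin against possible data loss and participant losses at each stage of the study".

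The available text does not attribute losses to a cause. It gives no denominator for the ceiling and does not say whether the ceiling applies per disease or overall, or whether the two rates are added together. It names no outcome other than pass or not pass.

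**The concern.** The 10% condition is justified as a check on the study, but its consequence falls on the device. Technical errors may be the software's doing. Data loss need not be: an image can fail to reach the software because of the camera, the operator or the file transfer. The Sample Size text treats data loss as something to be absorbed by extra participants, whereas the pass rule appears to treat it as a reason to fail the product.

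At stake is the meaning of the verdict. A not-passed result could reflect poor diagnostic performance, software faults or losses at the site, and the last of these says nothing about the study's objective.

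Pooling also works in the other direction. Software faults are tolerated up to just under 10%, and Annex 1 analyses a per-protocol population only. If faulted cases leave that population, they do not count against the device at all.

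**Working it through.** **Inputs.** 305 per disease (Annex 1, Sample Size); 915 participants (section 3, General Summary); a ceiling of strictly below 10% and thresholds of 90% (Annex 1, passing criteria); per-protocol analysis only (Annex 1, Analysis Population). Loss rates are not given and are assumed below.

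**The plan's own total.** 3 × 305 = 915, which agrees with section 3. The 305 comes from a kappa sample-size calculator whose inputs are not in the available text, so it is taken as given.

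**Where the ceiling is breached, counting participants.**

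- Per disease: 30/305 = 9.84% is allowed; 31/305 = 10.16% is a breach.
- Overall: 91/915 = 9.95% is allowed; 92/915 = 10.05% is a breach.

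Annex 1 defines sensitivity and specificity on eyes, and section 8 takes a right and a left image from each participant. Counting eyes, the trigger would be 61 of 2 × 305 = 610 per disease, or 183 of 2 × 915 = 1,830 overall (exactly 10%, hence not below it). The rule does not say which count applies.

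**Chance of a breach from losses unrelated to the software.** Assume each participant is lost independently with probability p, and that no loss is caused by the software.

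- Overall: P(X ≥ 92), X ~ Binomial(915, p).
- One disease group: q = P(X ≥ 31), X ~ Binomial(305, p).
- At least one of three groups: 1 − (1 − q)³.

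| True loss rate p | Overall (915) | One group (305) | Any of three groups |
|---|---|---|---|
| 5% | below 0.01% | 0.02% | about 0.05% |
| 7% | 0.04% | 2.5% | 7.2% |
| 8% | 1.5% | 10.2% | 27.5% |
| 9% | 14.6% | 26.5% | 60.3% |
| 10% | 49.4% | 49.0% | 86.7% |

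For example, at 8%: 1 − (1 − 0.1018)³ = 0.275.

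**A good device failed by the rule.** Suppose 31 of 305 are lost at the site, leaving 274. Taking the 90% threshold as applying to the point estimate (an assumption), the device needs at least 247 correct, since 0.9 × 274 = 246.6. With true accuracy of 95% it reaches that with probability 99.97%, but 31/305 breaches the ceiling. Under a split rule its software-fault rate would be 0/274, and only the three thresholds would decide.

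**The opposite direction.** Suppose 30 of 305 cases are lost to software faults, which is below the ceiling, and that these cases leave the per-protocol set. That leaves 275, and the smallest passing count is 248, since 0.9 × 275 = 247.5.

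- Faults excluded: 248/275 = 90.2%, a pass.
- Faults counted as errors: 248/305 = 81.3%, well short of 90%.

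**The case against.** **The ceiling may not be a pass criterion at all.** Annex 1 speaks of passing criteria only for accuracy, sensitivity and specificity. The 10% sentence is separate, garbled, and has its own purpose. The consequence could therefore refer back to the three thresholds alone. This stands as a possible reading. The ceiling is nevertheless mandatory and sits immediately before the consequence, so including it is the more natural reading. A verdict rule that can be read two ways needs settling before data are seen.

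**Participant losses may not count.** The Sample Size text names "possible data loss and participant losses at each stage of the study", so it lists the two kinds separately, while the ceiling names only technical errors and data loss. A reader might infer that 92 participants who drop out would fail the device; the documents do not establish that. The counts above apply to data loss with participants as the unit.

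**The probabilities depend on assumptions.** This stands. Only rates near 8% or above give a material risk, and the higher column needs a per-disease ceiling that the text does not state. A fault in the image archive would probably cluster, so independence is a simplification. Loss during the archive download is a possibility, not something the plan reports. Section 8 closes the study when the predicted number of data is reached, so losses might be replaced.

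**Reporting gives some protection.** A reader might infer that a failed verdict would be uninterpretable. That goes too far: Annex 1 already commits to sensitivity, specificity and accuracy with 95% confidence intervals and to tables for each disease, so poor diagnostic performance would be visible. What would remain hidden is whether losses came from the software or the site.

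**The rule is conservative.** This is true of failing a good device, but not of software faults that drop out of the per-protocol set.

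**Other sections may cover this.** Sections 9.3, 10.3, 11 and 13 appear as headings only in the available copy, so the absence of a split can be stated only for the text that can be read.

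**Conclusion.** The point holds as a defect in the decision rule. On its most natural reading, Annex 1 turns a breach of a study-reliability condition into failure of the software, whatever caused the loss. The alternative reading, in which only the three 90% thresholds decide, cannot be excluded, and that ambiguity in the primary verdict also needs correcting.

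With participants as the denominator, the trigger is data loss of 31 of 305 or 92 of 915. Under independent losses unrelated to the software, the chance of a breach is negligible at a true rate of 5%, 1.5% to 28% at 8%, and 49% to 87% at 10%. The lower figure applies the ceiling overall and the higher one applies it in each of three disease groups. These figures are a range over assumed rates and do not forecast that the device will be failed wrongly.

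The less conservative effect is conditional too. If software-faulted cases leave the per-protocol set, accuracy of 81.3% with faults counted as errors could be reported as 90.2%.

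**What to change.** In Annex 1:

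1. State that the three 90% thresholds, together with errors attributable to the software, decide whether the device passes.
2. State that data loss of 10% or more not caused by the software makes the study inconclusive and is not a device failure.
3. Define the denominator (eyes, images or participants), the level (per disease or overall), and whether participant losses count.
4. Log a cause for each lost image, assigned without knowledge of the reference result or of the software's accuracy.
5. Add a sensitivity analysis that counts software faults as errors, reported beside the per-protocol result.

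The cost is a few sentences, a reason code in the image log and one extra analysis. The downside is that assigning causes needs some judgement and could let software faults be relabelled as site loss; the blinding in item 4 is there to limit that. The 10% guard itself is kept.
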